## **5 SUBJECT SELECTION AND WITHDRAWAL**

### **5.1 Number of Subjects**

Up to 600 patients will be enrolled to obtain a minimum of two paired data points on 150 subjects.

### **5.2 Inclusion Criteria**

- Estimated 16 years of age or older or greater than or equal to 50 kg body weight if age unknown. (Adult trauma population includes patients 16 years of age and over at MHH).
- Level 1 (highest trauma activation) status at time of arrival to emergency department (ED).
- Expected to be admitted to the ICU/IMU for in hospital care.

### **5.3 Exclusion Criteria**

- Moribund patients with devastating injuries and expected die within one hour of ED admission.

- Prisoners, defined as those who have been directly admitted from a correctional facility (Prisoners are excluded because of their vulnerable population status. A free living individual who is under police observation as a suspect will remain in the study until hospital discharge).
- Obvious pregnancy in the ED (Pregnant women have a significantly increased intravascular volume and physiologic reserve for bleeding which can require adjustments to the standard treatment protocols therefore for consistency for analysis, pregnant women will be excluded).
- Received greater than 5 minutes of cardiopulmonary resuscitation (CPR) in the pre-arrival or hospital setting. (Patients who receive greater than 5 minutes of CPR are more likely to have non-survivable injuries and not likely to be admitted to the ICU for care).
- Has, on the ring, middle and index fingers of both hands, any of the following: finger deformities, injuries including burns, scar tissue or infection, or any material that may interfere with sensor application or trans-illumination of the site.
- Has significant bilateral trauma to the arms or forearms

#### **5.4 Subject Recruitment and Screening**

Upon presentation to the Emergency department, the clinical research staff will screen patients to determine eligibility based on the inclusion/exclusion criteria above. Patients who satisfy eligibility criteria will be enrolled.

#### **5.5 Informed Consent Process**

The study will be conducted utilizing a waiver of informed consent.

### **6 STUDY DEVICES**

Masimo Radical 7 pulse CO-Oximeter

Masimo Rainbow SpHb Sensors

Laptop [REDACTED]

#### **6.1 Device Accountability**

##### **6.1.1 Receipt of Study Device**

Upon receipt of the study device supplies, an inventory must be performed and the device accountability log filled out and signed by the person accepting the shipment. It is important that the designated study staff counts and verifies that the shipment contains all the items noted in the shipment inventory. Any damaged or unusable study devices in a given shipment will be documented in the study files. The investigator must notify the study sponsor of any damaged or unusable study devices that were supplied to the investigator's site.

##### **6.1.2 Use of Study Device**

Use of devices and sensors will be documented on case report forms for each subject.

##### **6.1.3 Return or Destruction of Study Device**

At the completion of the study, there will be a final reconciliation of study devices and sensors shipped, devices/sensors used, and devices/sensors remaining. This reconciliation will be logged on the device accountability log. Any discrepancies noted will be investigated, resolved, and documented prior to return or destruction of unused study devices. Devices destroyed on site will only be upon written instruction from the sponsor and will be documented in the study files.

### **7 STUDY PROCEDURES**

#### **7.1 Study Procedures**

Data collection will begin immediately within the first few minutes after admission to the emergency department. The SpHb butterfly sensor will be placed according to instructions in the manual of operations, [REDACTED] and connected to a time-synchronized Masimo Radical-7. Sensor placement will occur after the patient's position has been stabilized and after the secondary survey has been completed. The sensor will be placed, in order of preference, on the ring or middle finger of the non-dominant hand, the ring or middle finger of the dominant hand, the index finger of non-dominant hand, the index finger of the dominant hand. The sensor will not be placed on the thumb or the small finger, nor shall it be placed on any other location on the patient's body. The measurement site must be clean, have no deformity with any part of the finger including nail bed and have no trauma on the arm or forearm proximal to the site of sensor placement.

#### **7.2 Study Duration**

The Masimo Radical-7 will remain on the subject for up to the first 24 hours following ED admission or discharge from the ICU/IMU (whichever comes first). Direct subject observation will continue until 1) subject has arrived to the ICU/IMU following ED admission, 2) the subject expires or 3) 24 hours following ED admission or discharge from the ICU/IMU (whichever occurs first). Once direct observation is complete, the research team will continue to monitor the subject admitted to ICU (and had first a.m. lab draw completed) throughout the hospitalization to assess for additional procedures and complications incurred. For subjects who are not admitted to ICU/IMU and do not have a second sample drawn, additional data will be obtained through the trauma registry.

#### **7.3 Sample Collection**

Blood samples will be collected at time of ED admission and first a.m. lab draw in ICU. The blood samples will be based on clinical need and sent to at least two reference devices: the standard of care reference device for patient, hospital laboratory devices located at MHH, and a cyanomethemoglobin (HiCN) analyzer and a hematology analyzer located at a Masimo facility. For those subjects who have laboratory tests ordered at time of ICU admission, a third sample will be collected and sent to the CeTIR research lab for preparation for the cyanomethemoglobin analyzer at a Masimo facility. The collection of the HiCN and hematology analyzer samples must follow standard laboratory practices for handling of blood products as detailed in the manual of operations with at least 1 mL of blood being collected in an EDTA tube. Each sample will have a unique identifier with the identification key revealed by the site only after the sample has been processed by the Masimo analyzer. The exact time of sampling will be documented for retrospective analysis along with type (venous or arterial) and site of blood sampling, location of patient, time since presentation, and specific hospital laboratory analyzer used.

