### 1.1 Background and Rationale

The accurate measurement of circulating blood hemoglobin (Hgb) levels is one of the cornerstones of optimal treatment for traumatic injury and severe hemorrhage, the leading cause of death in people 1 to 40 years of age. In an autopsy study from the conflicts in Iraq and Afghanistan, fully 86% of all potentially preventable deaths were from truncal hemorrhage [Kelly 2008]. Likewise, in the civilian arena, the leading cause of potentially preventable death is early truncal hemorrhage [Demetriades 2004], with most deaths occurring within 6-12 hours of admission [Holcomb 2008, Clarke 2002, Moore 2008]. Measurement of Hgb requires blood to be drawn and subjected to laboratory analysis, resulting in delays of up to one hour before data are returned. This time lag can be critical in patients who have internal bleeding, a situation which can be difficult to detect even for an experienced clinician. Despite conventional teaching, the Hgb levels do change rapidly, and the first Hgb on admission to the hospital is highly predictive for blood loss. Thus, a portable, accurate, rapid, noninvasive measurement system is needed to improve quality and efficiency of treatment. In 2012, a study was conducted at Memorial Hermann Hospital (MHH) to evaluate Masimo's Radical-7, a non-invasive pulse co-oximeter, for Code 3 (highest acuity status) trauma patient during the first twenty four hours following patient presentation to the Emergency Department. One parameter measured by the device was the non-invasive Hgb (SpHb) and was compared to any laboratory Hgb (tHb) that was available for clinical care. The results of the study were recently published and it was found that while SpHb technology showed promise, it still required further refinement in order to be used for management of severely injured trauma patients [Moore 2013]. Since the conclusion of that study, the technology has continued to improve and the latest SpHb sensor revision has been designed to provide more accurate values in cases of varying oxygen saturation and in cases of large fluctuations in peripheral perfusion; the latter is often a compensatory or medically- induced physiological response which is often seen in trauma patient. Furthermore, a better understanding of the factors that may affect measurements of both tHb and SpHb may decrease inter-measurement variability and further improve the previously published performance.

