## **2 STUDY HYPOTHESIS**

SpHb can be used to identify bleeding patients sooner than standard of care by identifying critical drops between laboratory samples.

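### Critical drops that reverse between the named blood draws, and the lead time over standard of care, have no planned laboratory reference

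*Combined protocol and SAP*

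**What the plan says.** The hypothesis (section 2) is "SpHb can be used to identify bleeding patients sooner than standard of care by identifying critical drops between laboratory samples".

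Section 7.3 sets the reference samples: "Blood samples will be collected at time of ED admission and first a.m. lab draw in ICU". It adds that "The blood samples will be based on clinical need" and that "For those subjects who have laboratory tests ordered at time of ICU admission, a third sample will be collected". For these samples, "The exact time of sampling will be documented for retrospective analysis", together with sample type, site, patient location and the hospital analyzer used.

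Section 7.4 lists what is taken from the trauma registry and medical records. The list includes vital signs, blood products with their timing, procedures and complications. Laboratory hemoglobin values drawn for care are not on it.

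Section 7.5 says that a critical drop needs two or more laboratory values as reference and that the analysis will include 150 subjects with two or more samples. The size and time window of a critical drop are left to the interim analysis. Under section 7.2, SpHb is recorded for no more than 24 h after ED admission.

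Section 1.1 gives the background: hemoglobin can change fast, and early truncal hemorrhage is the leading preventable cause of death, "with most deaths occurring within 6-12 hours of admission". In the earlier study at the same hospital, SpHb "was compared to any laboratory Hgb (tHb) that was available for clinical care".

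**The concern.** The hypothesis is about what happens between laboratory samples and about who sees it first. Both parts need laboratory values inside the interval. With one value at each end, the laboratory shows only the net change.

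Two things are at stake. First, the primary categorical table needs a true state for each SpHb drop. If SpHb shows a drop that treatment has corrected by the morning, the reference cannot call it true or false, and the plan does not say which cell it enters. Second, a claim of earlier detection needs the time at which usual care first saw the drop. That time comes from the clinically ordered hemoglobin results, which the plan does not list for collection.

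The two-sample rule adds a selection effect. A subject who dies early with only the ED sample is not analyzed, and such subjects may include the bleeding patients the hypothesis is about.

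**Working it through.** The plan states no interval between the named draws, so there is no figure to reproduce. The check has three parts.

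**1. What each sample set can show (sections 7.3 and 7.5)**

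| Samples available | Count | Meets two-sample rule | Consecutive changes |
|---|---|---|---|
| ED, first a.m. | 2 | yes | 1 |
| ED, ICU admission, first a.m. | 3 | yes | 2 |
| ED, ICU admission, no a.m. | 2 | yes | 1 |
| ED only | 1 | no | 0 |

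Let H0 and H1 be two consecutive laboratory values and Hmin the lowest true value between them. The reference sees H1 − H0. The drop of interest is H0 − Hmin. If transfusion brings H1 back near H0, the reference shows little change however large H0 − Hmin was. This holds for any gap length. The conditional third sample shortens the interval for some subjects but does not remove the problem.

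**2. Lead time**

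Lead time = (time usual care first saw the drop) − (time SpHb first showed it). With only the named draws, the first term can be no earlier than the next named draw, even when an interim clinical result showed the drop sooner. A lead time computed that way is too long by the difference. If the drop has reversed by the next named draw, the first term does not exist.

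**3. How long the gap might be**

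All inputs here are assumptions: arrival pattern, hour of the a.m. draw, and T, the shortest time after arrival at which an a.m. draw in the ICU can count.

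*Uniform arrivals.* The gap is uniform from T to T + 24 h, so the share over 12 h is (12 + T)/24 and the mean is 12 + T.

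| T (h) | Share over 12 h | Mean gap (h) |
|---|---|---|
| 0 | 12/24 = 50% | 12 |
| 2 | 14/24 = 58% | 14 |
| 3 | 15/24 = 62.5% | 15 |
| 4 | 16/24 = 67% | 16 |
| 6 | 18/24 = 75% | 18 |

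Gaps above 24 h put the a.m. draw after SpHb recording has ended. Among gaps of 24 h or less, the share over 12 h is 12/(24 − T): 50% at T = 0, 57% at T = 3 and 67% at T = 6.

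*Other arrival windows* (uniform within the window, draw between 03:00 and 08:00, T of 0, 2 or 4 h):

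| Arrivals | Lowest share over 12 h | Highest share over 12 h |
|---|---|---|
| 18:00–02:00 | 0% (draw 06:00, gap 4–12 h) | 38% (draw 03:00, T = 4; 3 of 8 arrival hours wait for the next day) |
| 12:00–24:00 | 3/12 = 25% (draw 03:00, T = 0, gap 3–15 h) | 8/12 = 67% (draw 08:00, gap 8–20 h) |
| 06:00–18:00 | 9/12 = 75% (draw 03:00, gap 9–21 h) | 100% (draw 06:00, gap 12–24 h) |

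The share is 50% to 75% under uniform arrivals and anywhere from 0% to 100% across the other patterns. The arrival pattern drives the answer, and the documents do not give it.

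**The case against.** The strongest reply is that the plan is silent on interim values and does not exclude them. Sampling follows clinical need, samples go to the standard-of-care device, section 7.4 names medical records as a source, and section 7.5 speaks of laboratory values in general. The earlier study at this hospital used any clinical hemoglobin, so the authors may intend the same here, and a manual of operations that is not among these documents may say so. Clinically driven sampling also suits a non-interventional study run under a waiver of consent.

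Much of this stands, and it limits the point. A reader might infer that interim values are ruled out; no section says so. A reader might infer that section 7.5 judges drops only from ED to first a.m.; it contains no such restriction. A reader might infer that anyone without a morning draw is lost; a subject with ED and ICU-admission samples already qualifies. A reader might infer that an unconfirmed SpHb drop is scored as a false alarm; the plan does not say how it is scored.

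The silence itself does not stand as a defense. The reference for the primary metric has to be stated, and section 7.4 is detailed enough to list blood pressure cuff location while leaving out the values on which the hypothesis turns.

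**Conclusion.** The concern holds in limited form. Two draws are named for every subject and a third is conditional. As written, drops that reverse between those draws, and the lead time over usual care, have no planned laboratory reference. Subjects who die before the a.m. draw without an ICU-admission sample leave the analysis set; their number cannot be estimated from the documents. This should be corrected, but it does not by itself invalidate the study.

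The conclusion does not depend on the length of the gap. It is tempting to say that the two draws are usually more than 12 h apart. The documents do not support this: the 50% to 75% range assumes uniform arrivals, and other patterns give 0% to 100%. Nor is the hypothesis confined to the first hours. The 6 to 12 h figure is background on when deaths occur, and monitoring may run to 24 h.

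**What to change.** **Sections 7.3 and 7.4.** State that every laboratory hemoglobin drawn for clinical care while SpHb is recorded will be abstracted with its time, sample type and analyzer, and will serve as a reference point alongside the named draws.

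**Section 7.5.**
- Assess critical drops over each pair of consecutive laboratory values, with clustering by subject, because sicker patients will contribute more pairs.
- State that any two such values meet the two-sample rule, including in subjects who die before an ICU morning draw.
- Report SpHb drops with no laboratory value within a prespecified time as unverified, separately from false positives.
- Repeat the primary table as a sensitivity analysis on same-analyzer pairs or HiCN-only pairs.

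**Cost.** Abstraction of existing results from records already named as a source, plus analysis wording. No extra blood draw is needed.

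**Limits.** Interim values have no HiCN measurement, and differences between analyzers or between arterial and venous samples can create apparent drops; the sensitivity analysis is there for that reason. Drops that reverse between two clinical draws remain unseen.

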#### **7.4 Data Collection**

While the patient is in the Emergency Room, data will be collected and stored on a Radical-7. In the operating room and intensive care unit, data collection will be done using a Radical 7 connected to a laptop computer which will store live data [REDACTED]. All data will be properly labeled and downloaded to a server as soon as it is available for retrospective analysis.

Information to be collected will come from the trauma registry and medical records and will include subject demographics (gender, age, race/ethnicity), injury details (type of injury, severity, location on body), pre-hospital EMS care, initial ED care (blood products, life- saving interventions, vital signs), surgical and interventional radiology procedures, major complications (i.e. ARDS, sepsis, MOF), discharge location, number of hospital, ventilator and ICU days, and quantity and timing of blood product administration, anesthetics, changes in oxygenation, blood pressure cuff location, notes about any movements during surgery.

#### **7.5 Data Analysis**

This trial will provide baseline data on the performance of SpHb in a population with expected rapid changes in tHb levels. The primary metric to be measured is SpHb's ability to detect critical drops in a trauma population and present the data in a categorical table; statistical significance will be calculated with chi-squared analysis.

The secondary metrics that will be calculated include:

- 1- “Trend capability,” which will be determined by calculating the regression equation and coefficient of determination of a linear mixed effect regression model. The relative differences between data points will be represented graphically with polar plots [Critchley] and 4 quadrant plots.
- 2- Performance of different devices compared to HiCN values (the gold-standard for measuring hemoglobin concentration in blood), including the variability caused by standard of care laboratory devices.
- 3- Absolute accuracy calculation, which will be done by mean test method error with standard deviation, average root mean squared and graphically through Bland-Altman plots [Bland].

Analysis will be performed on the pooled data set as well as separate analyses on all data with high or low signal confidence respectively.

A total of 150 subjects with at least 2 blood samples will be included in the analysis. As a critical drop would require at least two laboratory data points for reference, the study will be powered in order to be 90% confident of achieving that target knowing that 47% of patients recruited in the previous study had at least two paired data points and that it is expected that 20% of patients will be excluded after enrollment (no data points).

An interim analysis will be performed after 50 cases with at least 2 blood samples per case have been completed. This will allow determination of the final sample size in order to obtain an appropriate definition of critical drop detection. The final sample size may be adjusted as a result of this analysis.

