## **3 STUDY DESIGN**

This is a prospective, non-blinded, non-randomized, non-interventional study of the Masimo pulse oximeter and sensors in a trauma setting.

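### The primary metric is detection of critical drops, but the only planned inference is a chi-squared test; no sensitivity, specificity or confidence interval for drop classification is prespecified.

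*Combined protocol and SAP*

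**What the plan says.** Section 7.5 sets the primary objective: "The primary metric to be measured is SpHb's ability to detect critical drops in a trauma population". The analysis attached to it is to "present the data in a categorical table; statistical significance will be calculated with chi-squared analysis". The section does not give the rows and columns of the table, the null hypothesis, a significance level or a performance target. Sensitivity, specificity, predictive values and confidence intervals for drop detection appear nowhere in the supplied text.

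The secondary metrics in the same section are more explicit:
- Metric 1 covers trending, by a linear mixed-effects regression with its coefficient of determination, and by polar and four-quadrant plots of relative differences.
- Metric 2 compares devices with the cyanomethemoglobin reference.
- Metric 3 is "Absolute accuracy calculation, which will be done by mean test method error with standard deviation, average root mean squared", with Bland-Altman plots.

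Three other statements set the context. The aim is descriptive: "This trial will provide baseline data on the performance of SpHb in a population with expected rapid changes in tHb levels". Section 3 says: "This is a prospective, non-blinded, non-randomized, non-interventional study". Section 2 gives the hypothesis: "SpHb can be used to identify bleeding patients sooner than standard of care by identifying critical drops between laboratory samples".

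**The concern.** Ability to detect is a matter of rates: the share of true drops that SpHb flags, set against the share of non-drops that it flags wrongly. A chi-squared test on the 2x2 table has independence as its null hypothesis, which is the same as sensitivity = 1 − specificity. Rejecting it says that SpHb flags and laboratory drops are related. It gives neither the detection rate nor its precision, and because the test is two-sided it does not give the direction.

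For a study whose stated product is baseline performance data, the detection rate and its interval are the useful result. As the plan stands, they would be calculated only if someone chose to do so after seeing the table. The choice of measure, of interval method and of the way to handle subjects with more than one interval would then be made with the data in hand.

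**Working it through.** **The plan's own figures.** None bears on detection. The one statement about powering, in section 7.5, concerns 90% confidence of obtaining 150 subjects with at least two samples. That is recruitment yield, not power for a test or precision of an estimate. From the documents I take only N=150.

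**Assumptions not in the documents.** The table is 2x2, each subject contributes one interval, the test is two-sided at 0.05, and 20% of intervals contain a critical drop (30 drops, 120 non-drops). A range of 10-30% is shown below.

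**Step 1: what the test returns.** With a = drops flagged, b = drops missed, c = non-drops flagged and d = non-drops not flagged, the uncorrected Pearson statistic is

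chi-squared = N(ad − bc)² / [(a+b)(c+d)(a+c)(b+d)].

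For the first row of the table below: 150 × (15×96 − 15×24)² / (30×120×39×111) = 150 × 1080² / 15,584,400 = 11.23.

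| Drops flagged | Non-drops flagged | Sensitivity | Specificity | Chi-squared | p |
|---|---|---|---|---|---|
| 15/30 | 24/120 | 50% | 80% | 11.23 | 0.0008 |
| 12/30 | 18/120 | 40% | 85% | 9.38 | 0.002 |
| 24/30 | 12/120 | 80% | 90% | 64.5 | <0.0001 |
| 3/30 | 48/120 | 10% | 60% | 9.63 | 0.002 |

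All four are significant. The third row is a good detector. The first two miss 50% and 60% of drops. In the fourth, SpHb flags 10% of drops but 40% of non-drops, which is worse than chance. The table would reveal that; the p-value would not.

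**Step 2: what the same table could give.** The exact (Clopper-Pearson) 95% limits for x of n are the 0.025 quantile of Beta(x, n−x+1) and the 0.975 quantile of Beta(x+1, n−x). For the first row:
- sensitivity 15/30 = 50% (31-69%)
- specificity 96/120 = 80% (72-87%)
- PPV 15/39 = 38% (23-55%)
- NPV 96/111 = 86% (79-92%)

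**Step 3: how often this would happen.** I summed binomial probabilities over all 2x2 tables with the number of drops fixed. For a true sensitivity of 50% at 20% drops, the probability of significance is 0.996, 0.90, 0.55, 0.18 and 0.05 at specificities of 90, 80, 70, 60 and 50%. At 80% specificity, over 10-30% drops, it is 0.71-0.96 for a sensitivity of 50%, 0.43-0.72 for 40% and 0.17-0.27 for 30%. Significance at low sensitivity is therefore common when specificity is fairly high, but it is not automatic.

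**Step 4: precision that the fix would report.** An observed sensitivity of 80% has an exact 95% interval of 52-96% with 15 drops (12/15), 61-92% with 30 (24/30) and 65-90% with 45 (36/45).

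**The case against.** Four arguments can be made for the plan.

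First, a reader might infer that the p-value is irrelevant to the primary metric. That goes too far. The null of sensitivity = 1 − specificity means no discrimination, so the test does ask whether any association exists. At 50% sensitivity and 50% specificity it rejects only about 5% of the time, and a device at 50% and 80% does discriminate (positive likelihood ratio 0.50/0.20 = 2.5). This argument stands. What is missing is the size of the effect, not all relevance.

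Second, the plan includes a table as well as a test, and on the 2x2 reading sensitivity, specificity and direction follow from its cells. This also stands, but being derivable afterwards is not the same as being prespecified with an interval. A reader might also infer that the report will lead with a significance claim. The documents say nothing about how results will be presented, so that is not part of the point.

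Third, the secondary metrics already cover performance. They do so in part: metric 1 addresses whether SpHb changes track laboratory changes, and metric 3 addresses absolute values. Neither gives a missed-drop or false-flag rate.

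Fourth, the study is non-interventional and states no significance level or success criterion, so no documented decision turns on the p-value. This is correct, and it limits the harm to the interpretation and prespecification of the primary result.

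**Conclusion.** The concern holds in this form: a two-sided test of association is planned for a primary metric that is about detection, and no estimate or interval for drop classification is prespecified. It should be fixed. It does not invalidate the study, because the data needed are the ones already planned.

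The size is illustrative. With 150 subjects and an assumed 30 drops, p=0.0008 is compatible with missing half of the drops, and p=0.002 with a device worse than chance. These figures rest on the 2x2 layout, one interval per subject and the assumed counts of drops and flags. The documents supply only the 150. That significance does not measure detection is a general property of the test and does not depend on those counts.

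A reader might take the study hypothesis to be settled either by the chi-squared test or by the analysis proposed below. Neither does that: the claim of earlier identification than standard of care is about timing, and this table does not contain it.

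**What to change.** In section 7.5:
- Make the primary analysis the sensitivity and specificity, with PPV and NPV, of an SpHb-defined drop against the laboratory-defined critical drop, each with a 95% confidence interval.
- State the table's axes and the unit of analysis (subject or between-sample interval).
- Use exact intervals if each subject contributes one interval. Section 7.3 allows for more: "For those subjects who have laboratory tests ordered at time of ICU admission, a third sample will be collected". If such subjects contribute two intervals, use a cluster bootstrap or GEE by subject, since an ordinary chi-squared test or exact interval would treat them as independent.
- Keep the chi-squared p-value as descriptive.

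The change presupposes a fixed definition of critical drop. Section 7.5 ties that to the interim analysis, whose purpose is to settle the sample size "in order to obtain an appropriate definition of critical drop detection". The chi-squared table needs the same definition, so this is not an extra burden. The timing element of the hypothesis needs its own analysis or should not be claimed from this table.

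The cost is a revision of the wording in section 7.5 and a few lines of code on the same table, with no new data. The downside is a result that may look less favourable than a small p-value, with a wide sensitivity interval if drops are few.

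### The only primary test puts the continuous SpHb reading into categories at an unstated cut-off; an ROC area with its confidence interval should stand beside the table as the test of discrimination

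*Combined protocol and SAP*

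**What the plan says.** The study hypothesis (section 2) is that "SpHb can be used to identify bleeding patients sooner than standard of care by identifying critical drops between laboratory samples". Section 7.5 turns this into a primary metric, SpHb's "ability to detect critical drops in a trauma population", and the instruction for it is to "present the data in a categorical table; statistical significance will be calculated with chi-squared analysis". No other primary test is named. The section does not state the SpHb cut-off, the number of categories, the laboratory threshold for a critical drop, the significance level or a target accuracy. It leaves the definition of critical drop detection to an interim analysis after 50 cases.

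The analysis set is given as "A total of 150 subjects with at least 2 blood samples will be included in the analysis". Uncut SpHb values are used only in the secondary metrics: mixed-effects regression with polar and four-quadrant plots for trend, and bias, standard deviation, root mean square error and Bland-Altman plots for agreement.

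**The concern.** The laboratory drop has to be yes or no, because it is the event to be detected. SpHb does not have to be cut for the test. Sections 1.2 and 7.4 describe a continuous monitor whose live data are stored. Once its change is reduced to classes, a reading just past the cut counts the same as one far past it, and one just short of the cut counts the same as no change at all.

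Two things are at stake. First, critical drops may be few among 150 subjects (15 at an assumed 10% prevalence, 30 at 20%), so discarded information can be costly. Second, the single primary p-value depends on an SpHb cut-off that is not written down, and another cut-off could give another answer. An ROC area uses every SpHb cut-off and so does not depend on the choice of one.

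**Working it through.** **The plan's own figure.** The only power-like statement is that "the study will be powered in order to be 90% confident of achieving that target", meaning 150 subjects with at least two samples. It rests on the statement that "47% of patients recruited in the previous study had at least two paired data points" and on 20% exclusion after enrollment. The evaluable share is 0.47 × 0.80 = 0.376. By the exact binomial, 432 enrolled give a 90.1% chance of at least 150 evaluable, and 431 give 89.5%. The stated 600 is a cap, at which 0.376 × 600 ≈ 226 evaluable would be expected. This concerns recruitment yield. The documents give no power for the chi-squared test, so there is no stated power to reproduce.

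**Inputs for the comparison.** From section 7.5: 150 subjects. Assumed, because not stated: two-sided 5%; one change per subject; laboratory and SpHb changes bivariate normal with correlation ρ; drop prevalence 10, 20 or 30%; SpHb cut in two at the same percentile as the laboratory drop. Tests: Pearson chi-squared on the 2×2 table, and the Wilcoxon (Mann-Whitney) test of SpHb change between drop and no-drop subjects. The Mann-Whitney statistic U gives the ROC area as AUC = U/(n₁n₀).

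**Simulated power, chi-squared against Wilcoxon, and the loss in percentage points**

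| ρ | 10% prevalence | 20% | 30% |
|---|---|---|---|
| 0.1 | loss 0 | loss 3 | loss 2 |
| 0.2 | 20 v 28 (8) | 26 v 38 (12) | 31 v 44 (13) |
| 0.3 | 37 v 55 (18) | 51 v 72 (21) | 59 v 79 (20) |
| 0.4 | 58 v 80 (22) | 76 v 93 (17) | 85 v 96 (11) |
| 0.5 | loss 18 | loss 7 | loss 3 |
| 0.6 | loss 8 | loss 1 | loss 0 |
| 0.7 | loss 2 | loss 0 | loss 0 |
| 0.8 | loss 0 | loss 0 | loss 0 |

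Repeat runs agree to within about 2 points. With no association both tests reject in about 4 to 6% of runs, so the gap is not bought with a higher false-positive rate.

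**Sample-size equivalent at ρ = 0.3 and 20% prevalence.** Powers of 51% and 72% correspond to 1.96 + 0.03 = 1.99 and 1.96 + 0.58 = 2.54. The ratio (2.54/1.99)² ≈ 1.6, so the chi-squared test would need about 1.6 times as many subjects for the same power.

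**Hand check by formula.** Take 20% prevalence (n₁ = 30, n₀ = 120) and a 0.5 SD difference in mean SpHb change.
- Continuous: SE = √(1/30 + 1/120) = 0.204; 0.5/0.204 = 2.45; power = Φ(2.45 − 1.96) = 69%.
- Cut midway: 60% of drop subjects and 40% of the others are flagged. Pooled proportion 0.44; null SE = √(0.44 × 0.56) × 0.204 = 0.101; alternative SE = 0.100; power = Φ((0.197 − 1.96 × 0.101)/0.100) ≈ 50%.
- Loss: 19 points.

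**A badly placed cut.** At 20% prevalence, an SpHb cut that flags only 5% of subjects costs about 38, 42 and 29 points at ρ = 0.3, 0.4 and 0.5.

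**The case against.** The strongest reply is that detection is a yes/no matter. A clinician needs a rule, the hypothesis is about identifying patients, and a table at a declared cut-off answers that directly. An ROC area averages over cut-offs that nobody would use, and a significant Wilcoxon test shows only that the area differs from 0.5. This stands as a reason to keep the table. It does not support a chi-squared p-value as the only primary test, because that p-value also shows association rather than detection accuracy.

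A second reply is that the large losses arise where SpHb is a poor detector. At 20% prevalence and ρ = 0.3 the model gives sensitivity of about 33% and an AUC of about 0.65; at ρ = 0.4, about 38% and 0.70. At ρ = 0.6 to 0.7 (AUC about 0.80 to 0.85 or more), chi-squared already has about 90% power or more even at 10% prevalence. This stands and limits the size of the point. Strong tracking cannot be taken for granted, however: section 1.1 reports that the earlier trauma study at the same hospital found the technology still in need of refinement.

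Third, the secondary metrics already use continuous SpHb. They do, but for trend and agreement. Neither measures how well SpHb change separates subjects with a critical drop from those without.

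Fourth, the plan does not say that SpHb is cut into exactly two classes; a table with more levels would lose less. The study is also described as providing baseline data, and its size may be revised at the interim. All of this is fair, and it is why the loss is given as an assumed range.

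A reader might infer that the plan forfeits a fixed 10 to 20 points of power, or that the trial is underpowered. The documents support neither. They contain none of the inputs needed, and the range reaches zero at both weak and strong correlation.

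**Conclusion.** The point holds as one of analysis choice. The only primary test works on categorised SpHb, discards information that the device records, and depends on a cut-off that the plan does not state. The power cost is conditional: about 0 to 25 percentage points at 150 subjects with a matched two-class cut, greatest at correlations of about 0.3 to 0.5, near zero at 0.7 or above, and larger if the cut is badly placed. These figures rest on bivariate normal changes, one change per subject, two-sided 5% and prevalence of 10 to 30%, all assumed.

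It would go too far to say that the categorical table is wrong or should be replaced. The primary question is detection, and removing the table would change what is being estimated.

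**What to change.** In section 7.5, add to the primary analysis the area under the ROC curve of SpHb change between paired draws for the laboratory-defined critical drop, with its 95% confidence interval (Wilcoxon form), and name it as the test of discrimination. State the significance level. Keep the categorical table as the co-reported detection result, with sensitivity and specificity at an SpHb cut-off fixed before the analysis.

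The cost is a few sentences in the plan, with the same subjects and data. There are two limits. An ROC area is not a decision rule, which is why the table stays. And it removes the dependence on the SpHb cut-off only: the laboratory definition of a critical drop must still be set in advance.
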